**Figure 3.1 The results of a FAST Plasma Volume Measurement Volume Challenge Test in a healthy dog model.**

### 3.4.2 First-in-Human Study

A FIH study, representing the first human use of the VFI, was concluded in 2012. Data from the study indicated that the FAST PV and mGFR Technology is safe and well tolerated. In this study, 32 subjects were enrolled with 8 subjects (6 VFI + 2 placebo) assigned to 1 of 4 dose groups. The VFI agent consisted of a mixture of 2 different molecular weight carboxymethyl dextran molecules (5 kD [FD001] and 150 kD [FD003]) with different fluorescent dye molecules attached. Four increasing doses were administered through a bolus injection: Group 1, 5 mg/0.1 mL VFI; Group 2, 15 mg/0.3 mL VFI; Group 3, 75 mg/1.5 mL VFI; Group 4, 150 mg/3 mL VFI.

All 32 subjects completed the study as planned and were included in the safety analysis. Overall 9 subjects (28.1%) experienced 15 treatment-emergent adverse events (TEAEs) which were considered by the investigator to be reasonably related to VFI administration or study procedures. Most related TEAEs were observed after administration of 15 mg VFI (9 TEAEs reported by 3 subjects). No related TEAEs were observed after the highest dose. Only 2 subjects (both 15 mg VFI) reported 6 TEAEs (pruritus and gastrointestinal disorders) which were considered related to VFI administration. All other related TEAEs were judged to be related to

CONFIDENTIAL

the study procedures (mainly injection site pain and hematoma at the blood sampling site). All TEAEs were of mild to moderate intensity. There were no serious adverse events (SAEs); no subject discontinued the study due to adverse events (AEs). Safety laboratory parameters, vital signs, and electrocardiogram (ECG) parameters showed no clinically relevant time- or treatment-related effects or differences between dose groups.

All subjects who received VFI were included in the PK analysis. Geometric mean AUC and  $C_{max}$  of FD001 and FD003 increased dose-proportionally. FD001 had a median time at which the maximum concentration was observed ( $t_{max}$ ) of 0.25 hours for all doses; median  $t_{max}$  of FD003 was about 0.5 hours for the 2 lower doses and 2 hours for the 2 higher doses. FD001 was eliminated with a short elimination half-life ( $t_{1/2}$ ) of about 1.5 to 4 hours; mean  $t_{1/2}$  for FD003 was considerably longer ranging from 47 to 111 hours. Detailed PK data is available in the Investigator's Brochure for this study.

### 3.4.3 Phase 2a Study at University of Alabama at Birmingham

For the Phase 2a study completed in 2015 at the University of Alabama at Birmingham, 5 cohorts with a total of 33 patients were studied. The primary endpoint of the study was to establish safety of the IV administered VFI. This end point was achieved, and even with increasing severity of CKD, with its associated comorbidities, no SAEs were reported during the study. A relatively small number of AEs were reported as potentially related to the VFI. The FAST BioMedical measured GFR (mGFR) was evaluated by performing an Iohexol study along with standard estimates of GFR using creatinine and cystatin C values and both Modification of Diet in Renal Disease (MDRD) and Chronic Kidney Disease Epidemiology Collaboration (CKD-EPI) equations. The breakdown of patients and GFR ranges in each cohort is listed in [Table 3.2](#).

Both Iohexol and the FAST mGFR technologies utilized timed blood draws and subsequent concentrations to calculate a predicted total AUC. The dose of marker given was divided by this AUC to calculate the mGFR, with scaling based on body surface area. The FAST mGFR utilized 3 blood draws taken at early time points out to 2 hours. A fourth virtual point was calculated based on the PV at T0 (the starting concentration in the plasma just after the dose is given or time 0). The Iohexol GFR 6 test utilized a blank, plus a minimum of 6 additional blood draws taken over 6 hours to determine the AUC. Iohexol, having a much smaller molecular size, distributes differently within the extracellular space, so some difference in mGFR between the 2 markers was anticipated. FAST BioMedical expected to measure mGFR values slightly lower than Iohexol in normal patients, as most single marker systems like Iohexol have difficulty resolving the early decay phase when the clearance is rapid. It was expected that the FAST mGFR measurements would be within 10% in the lower GFR groups. Prior studies conducted by FAST BioMedical using both the VFI and Iohexol in anesthetized dogs, have shown there were differences between the 2 methods. Analysis of the single marker decay rate showed that it normally resolved to a falsely high volume of distribution making the resulting mGFR biased higher than the FAST 2 marker system, which quantifies the initial volume of marker distribution. This small error in AUC was only significant in mGFRs above 80 mL/min.

In addition to studying a range of GFRs using different measurement techniques, FAST BioMedical intended to evaluate FAST’s measured PV method against a standard clinical estimate of PV, specifically Nadler’s Formula (Nadler et al 1962).

$$\text{Plasma Volume (males)} = 0.3669 \times (\text{Height [m]})^3 + 0.03219 \times (\text{Body Weight [kg]}) + 0.6041$$

$$\text{Plasma Volume (females)} = 0.3561 \times (\text{Height [m]})^3 + 0.03308 \times (\text{Body Weight [kg]}) + 0.1833$$

CONFIDENTIAL

The difference between a measured and estimated PV are between plus 20% to minus 30% ([Feldschuh and Enson, 1977](#)) using radioiodinated human serum albumin as the measured plasma marker. Since Nadler's work was based primarily on measurements in healthy subjects, it was expected there may be a greater range seen with the CKD population in this study.

Pharmacokinetic data analysis was performed on Cohorts 2, 3 and 5. The results indicated that the VFI performed as expected over the course of the study and corresponded well to the measured renal function and PV of the subjects.

Following administration of 75 mg VFI by IV bolus injection to adults with preserved kidney function and impaired kidney function it was concluded that the mean plasma concentrations of FD001 exhibited little variability within study groups for samples collected from 0.25 to 24 hours. Plasma FD001 concentrations generally reached  $C_{max}$  following the end of the infusion and decreased in a multi-exponential, first-order elimination manner with early-phase distribution apparently complete at 8 to 12 hours and measureable concentrations observed in all subjects at 24 hours. Median plasma FD001  $t_{max}$  values were 0.25 hours, the time of the first post administration sample collection in all study groups. Mean plasma FD001  $t_{1/2}$  estimates were 5.64, 9.48, and 18.3 hours for Groups 5, 2, and 3, respectively, increasing with decreasing renal function. Mean FD001 CL decreased with decreasing renal function. No significant differences between groups were observed in FD001  $C_{max}$  ( $p = 0.6751$ ),  $t_{max}$  ( $p = 0.7418$ ),  $V_{ss}$  ( $p = 0.8425$ ), or  $C_{max}/Dose$  ( $p = 0.4781$ ); and anticipated differences were observed in FD001  $AUC_{last}$  ( $p < 0.0001$ ),  $t_{1/2,z}$  ( $p = 0.0015$ ), CL ( $p < 0.0001$ ), and  $AUC_{inf}/Dose$  ( $p < 0.0001$ ).

Following administration of 75 mg VFI by IV bolus injection to adults with preserved kidney function and impaired kidney function, mean plasma FD003 concentrations exhibited little variability within study groups for samples collected from 0.25 to 504 hours. Plasma FD003 concentrations reached maximum concentrations within 1 hour in all study groups and decreased in a mono-exponential, first-order elimination manner with measureable concentrations observed in all subjects at 504 hours. The observed half-life of FD003 ranged from 90 hours for healthy subjects to 125 hours for patients with severely impaired kidney function (eGFR  $\geq 15$  and  $< 30$  mL/min/1.73 m^2) and were generally similar irrespective of renal function. Mean FD003 volume estimates indicated that FD003 appeared to occupy a volume space that corresponds with PV. Mean FD003 CL did not change with decreasing renal function. No significant differences were observed in FD003  $C_{max}$  ( $p = 0.0743$ ),  $t_{max}$  ( $p = 0.0600$ ),  $AUC_{last}$  ( $p = 0.8469$ ),  $AUC_{inf}$  ( $p = 0.8684$ ),  $t_{1/2,z}$  ( $p = 0.0508$ ),  $V_z$  ( $p = 0.2644$ ),  $V_{ss}$  ( $p = 0.3305$ ), CL ( $p = 0.5048$ ),  $C_{max}/Dose$  ( $p = 0.1652$ ), or  $AUC_{inf}/Dose$  ( $p = 0.5048$ ). A delay in the dispersion of the FD003 molecule initially after dosing resulting in a later than anticipated  $C_{max}$ . Complete PK data for the Phase 2a study is located in the Investigator's Brochure from this study.

### 3.5 Iohexol Background

OMNIPAQUE™ 300 (hereafter referred to as Iohexol) is indicated in adults for aortography including studies of the aortic arch, abdominal aorta and its branches, contrast enhancement for

CONFIDENTIAL

computed tomographic head and body imaging, cerebral arteriography, peripheral venography (phlebography), and excretory urography.

Following intravascular injection, Iohexol is distributed in the extracellular fluid compartment and is excreted unchanged by glomerular filtration. It will opacify those vessels in the path of flow of the contrast medium permitting radiographic visualization of the internal structures until significant hemodilution occurs.

Approximately 90% or more of the injected dose is excreted within the first 24 hours, with the peak urine concentrations occurring in the first hour after administration. Plasma and urine Iohexol levels indicate that the Iohexol body clearance is due primarily to renal clearance (CLr). An increase in the dose from 500 to 1500 mgI/kg does not significantly alter the clearance of the drug. The following PK values were observed following the IV administration of Iohexol (between 500 to 1500 mgI/kg) to 16 adult human subjects: CLr, 120 (86 to 162) mL/min; total body clearance (CL), 131 (98 to 165) mL/min; and volume of distribution, 165 (108 to 219) mL/kg.

Renal accumulation is sufficiently rapid that the period of maximal opacification of the renal passages may begin as early as 1 minute after IV injection. Urograms become apparent in about 1 to 3 minutes with optimal contrast occurring between 5 to 15 minutes. In nephropathic conditions, particularly when excretory capacity has been altered, the rate of excretion may vary unpredictably, and opacification may be delayed after injection. Severe renal impairment may result in a lack of diagnostic opacification of the collecting system and, depending on the degree of renal impairment, prolonged plasma Iohexol levels may be anticipated. In these patients, the route of excretion through the gallbladder and into the small intestine may increase.

Iohexol displays a low affinity for serum or plasma proteins and is poorly bound to serum albumin.

No significant metabolism, deiodination, or biotransformation occurs.

Iohexol enhances computed tomographic imaging through augmentation of radiographic efficiency. The degree of density enhancement is directly related to the iodine content in an administered dose; peak iodine blood levels occur immediately following rapid IV injection. Blood levels fall rapidly within 5 to 10 minutes and the vascular compartment half-life is approximately 20 minutes. This can be accounted for by the dilution in the vascular and extravascular fluid compartments which causes an initial sharp fall in plasma concentration. Equilibration with the extracellular compartments is reached in about 10 minutes; thereafter, the fall becomes exponential.

Refer to the [OMNIPAQUE \(Iohexol\) injection prescribing information \(2010\)](#) for additional details.

CONFIDENTIAL

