**Criteria for Evaluation:****Safety:**

Adverse events (AEs) will be collected and evaluated as they occur throughout the study. Safety assessments, including physical examinations, vital signs including pulse oximetry assessments, 12-lead ECGs, and clinical laboratory tests, will be performed at specified time points.

**Pharmacokinetics:** Pharmacokinetic samples for plasma FD001 and FD003 concentration determination in Cohort 1 will be collected predose and 15, 30, 60, 120, 165, 195, 205, 310, 370, and 480 minutes and 12 and 24 hours post VFI dose. Pharmacokinetic samples for plasma FD001 and FD003 concentration determination in Cohort 2 will be collected predose and 15, 30, 60, 120, 170, 310, 370, and 480 minutes, 12 and 24 hours post VFI dose on Days 1 and 2, and on Days 5 ( $\pm$  1 day), 9 ( $\pm$  1 day), 16 ( $\pm$  1 day), and 22 ( $\pm$  1 day). Pharmacokinetic samples for plasma FD001 and FD003 concentration determination in Cohorts 3 and 4 will be collected predose and 15, 30, 60, 120, 170, 310, 370, and 480 minutes, 12, 24, and 32 hours post VFI dose, and on Days 4 ( $\pm$  1 day), 8 ( $\pm$  1 day), 15 ( $\pm$  1 day), and 21 ( $\pm$  1 day). Pharmacokinetic samples for urine FD001 concentration determination in Cohorts 2 through 4 will be collected predose, from dosing (0 hour) to 2 hours postdose, and from 2 to 12 hours postdose. Subjects in Cohort 2 receiving a second VFI dose on Day 2 will follow the same urine collection schedule as Day 1.

Plasma concentrations of FD001 and FD003 will be determined using a validated fluorometric assay.

CONFIDENTIAL

**Criteria for Evaluation:** Urine concentrations of FD001 will be determined using a validated method and concentration of FD001 will be multiplied by urine volume to determine the amount of excreted FD001.

The following PK parameters will be calculated from the plasma and urine concentration/volume data using noncompartmental methods and actual sampling times:  $C_{max}$ ,  $t_{max}$ ,  $AUC_{0-12}$  (FD001 only),  $AUC_{last}$ ,  $AUC_{inf}$ ,  $t_{1/2}$ ,  $\lambda_z$ ,  $CL$ ,  $CL_{r0-2}$  (FD001 only),  $CL_{r2-12}$  (FD001 only),  $CL_{r0-12}$  (FD001 only),  $V_z$ ,  $V_{ss}$ ,  $Ae_{0-2}$ ,  $Ae_{0-12}$ .

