Study Day	Time (Relative to Start of VFI Bolus Injection)	FD001 and FD003 PK/PD Plasma Sample	FD001 PK Urine Sample	Time (Relative to Start of Iohexol Bolus Injection)	Iohexol PD Plasma Sample		
1	Predose	X	X a	Predose	X		
	0 minutes		VFI Administration				
	15 minutes	X		-	-		
	30 minutes	X		-	-		
	60 minutes	X		-	-		
	120 minutes	X		-	-		
	160 minutes		Iohexol Administration				
	170 minutes	X		10 minutes	X		
	280 minutes	-		120 minutes	X		
	310 minutes	X		150 minutes	X		
	340 minutes	-		180 minutes	X		
	370 minutes	X		210 minutes	X		
	480 minutes	X		320 minutes	X		
	12 hours	X		560 minutes	X		
2	24 hours	X		-	-		
	32 hours	X		-	-		
4	72 hours	X		-	-		
8	168 hours	X		-	-		
15	336 hours	X		-	-		
21	480 hours	X		-	-		

Abbreviations: PD = pharmacodynamic; PK = pharmacokinetic; VFI = visible fluorescent injectate

a. Patients will be asked to void their bladder prior to VFI dosing; a small sample (~10mL) will be saved.  
 b. Urine will be collected from time 0 through 2 hours and pooled and from 2 hours through 12 hours and pooled.  
 A total volume of urine in each pool will be measured. Patients will be asked to void their bladder at the 2-hour and the 12-hour time point. Time of void should be recorded.

Note: Blood samples may not be collected from the same arm used for VFI administration. In the event that vascular access cannot be established in both arms, a single arm may be used with documentation in the patient records. PK/PD blood samples will be collected as close to the nominal time point as possible. Allowable windows for PK/PD blood sample collection relative to dosing will be as follows: within 30 minutes predose,  $\pm$  1 minute through 170 minutes postdose,  $\pm$  2 minutes through 480 minutes postdose,  $\pm$  10 minutes through 24 hours postdose,  $\pm$  1 hour through 32 hours postdose and  $\pm$  1 day through Day 21. In the event samples for VFI and Iohexol are scheduled to be taken at the same time, VFI samples should be taken first, followed by Iohexol samples.

CONFIDENTIAL

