**Table 5.1      Planned Dose Cohorts**

Cohort	eGFR	VFI Dose	Number of Doses	Comparator Dose	Number of Doses	Number of Subjects
1*	≥ 60 mL/min/1.73 m 	47 mg/3 mL	1	---	---	Up to 8
2	≥ 60 mL/min/1.73 m 	47 mg/3 mL	2	Iohexol 5 mL	1	Up to 8
3	≥ 30 and < 60 mL/min/1.73 m 	47 mg/3 mL	1	Iohexol 5 mL	1	Up to 8
4	≥ 15 and < 30 mL/min/1.73 m 	47 mg/3 mL	1	Iohexol 5 mL	1	Up to 8

\*Subjects in Cohort 1 will receive a volume challenge

Cohort 1:

Eligible subjects ≥ 50 kg in weight will receive a single dose of VFI followed 130 minutes later by a 350 mL infusion of 5% albumin over 30 minutes on Day 1. Eligible subjects < 50 kg in weight will receive a single dose of VFI followed 130 minutes later by a maximum infusion of 5% albumin of 7 mL/kg over 30 minutes on Day 1. Subjects will remain resident in the CRU for at least 24 hours after VFI administration for safety, PK, and PD assessments. Subjects will return to the CRU for an end-of-study (EOS) visit on Day 21 (± 1 day).

Cohort 2:

Eligible subjects will receive a dose of VFI followed 160 minutes later by a single dose of Iohexol on Day 1 and a second dose of VFI 24 hours following the initial dose of VFI. Subjects will remain resident in the CRU for at least 24 hours after the second VFI administration for safety, PK, and PD assessments. Subjects will return to the CRU for follow-up visits on Days 5 (± 1 day), 9 (± 1 day), and 16 (± 1 day) and an EOS visit on Day 22 (± 1 day).

Cohorts 3 and 4:

Eligible patients will receive a single dose of VFI followed 160 minutes later by a single dose of Iohexol on Day 1.

Patients enrolled into Cohort 3 at ICON Early Phase Services will remain resident in the CRU for at least 24 hours after VFI administration for safety, PK, and PD assessments. Patients will return to the CRU for follow-up visits on Days 4 (± 1 day), 8 (± 1 day), and 15 (± 1 day), and an EOS visit on Day 21 (± 1 day).

Patients enrolled into Cohorts 3 or 4 at UAB will remain in the CRU through the 12-hour sample collection after VFI administration for safety, PK, and PD assessments. Patients will stay at a local hotel near the CRU and will return to the CRU on Day 2 for 24-hour sample collection. Patients will return to the CRU for follow-up visits on Days 4 (± 1 day), 8 (± 1 day), and 15 (± 1 day), and an EOS visit on Day 21 (± 1 day).

Refer to [Table 2.1](#), [Table 2.2](#), and [Table 2.3](#) for the Schedules of Assessments and Procedures.

CONFIDENTIAL

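### In Cohort 4, iohexol sampling ends 560 minutes after injection; assaying the already scheduled 24 h draw for iohexol would cheaply sharpen the reference GFR

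*Protocol*

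**What the plan says.** Protocol Section 5.1 gives Cohorts 3 and 4 one VFI dose, "followed 160 minutes later by a single dose of Iohexol on Day 1". Table 2.6, repeated as SAP Table 1.6, schedules iohexol plasma at predose and at 10, 120, 150, 180, 210, 320 and 560 minutes after iohexol. These are the times that Table 2.5 uses for healthy Cohort 2.

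The synopsis (Criteria for Evaluation) lists VFI plasma in Cohorts 3 and 4 at "480 minutes, 12, 24, and 32 hours post VFI dose". In Table 2.6 the 24 h and 32 h rows carry an FD001/FD003 sample and a dash for iohexol. The note to that table already covers shared draws: "In the event samples for VFI and Iohexol are scheduled to be taken at the same time, VFI samples should be taken first".

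Protocol Section 3.5 states that in severe renal impairment "prolonged plasma Iohexol levels may be anticipated", and gives iohexol PK from 16 adults, including "volume of distribution, 165 (108 to 219) mL/kg". No value is given for renal impairment.

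For this study the documents name the iohexol clearance test (Protocol 8.5.1.2, SAP 9.2.1.2) and plan correlation and Bland-Altman plots against FAST mGFR, the latter in each cohort (SAP 10.1.10.2). They define no iohexol AUC or clearance formula, no terminal-phase rule and no limit on extrapolation. Section 3.4.3 describes the Phase 2a method as dose over a predicted total AUC.

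**The concern.** Iohexol is the only other measured GFR against which FAST mGFR is compared. In a Bland-Altman plot, error in the reference widens the limits of agreement just as error in FAST does, and a reader will tend to charge the whole width to FAST. At low GFR iohexol falls slowly, so a schedule that is ample in healthy subjects covers much less of the curve. The terminal slope, and with it the reference clearance, is then less well determined in the cohort that is plotted on its own with at most 8 patients.

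The protocol adapts VFI sampling to renal impairment, since the 32 h draw appears only in Cohorts 3 and 4, but it leaves the iohexol times unchanged. Once the 24 h plasma has been discarded, the information cannot be recovered.

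**Working it through.** The plan states no extrapolated share and no iohexol precision, so there is no figure of its own to reproduce.

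**Inputs from the documents.** Last iohexol sample 560 min. Iohexol given 160 min after VFI, so 24 h is 1440 − 160 = 1280 min after iohexol, and 32 h is 1920 − 160 = 1760 min. Cohort 4 eGFR 15 to below 30 mL/min/1.73 m². Volume 165 (108 to 219) mL/kg. Total clearance 131 and renal clearance 120 mL/min, a difference of 11 mL/min. Decline exponential after about 10 minutes (Section 3.5).

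**Assumptions.** Weight 60 to 100 kg (the documents give only a 40 kg minimum). GFR used directly as clearance in mL/min. Assay error 2-5%. Estimator as in step 2.

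**Step 1: share of AUC beyond the last sample.** For one compartment, share = exp(−CL × t / V). Example at 80 kg: V = 0.165 × 80 = 13.2 L; at CL 15, exp(−15 × 560 / 13200) = 52.9%.

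| Weight (165 mL/kg) | To 560 min, GFR 29 / 15 | With 24 h draw, GFR 29 / 15 |
|---|---|---|
| 60 kg | 19% / 43% | 2% / 14% |
| 70 kg | 24% / 48% | 4% / 19% |
| 80 kg | 29% / 53% | 6% / 23% |
| 100 kg | 37% / 60% | 10% / 31% |

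Adding the 32 h draw at 80 kg brings the share to 2% / 13.5%.

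Sensitivity:
- Volume, at 70 kg and GFR 30 to 15: 11-33% at 108 mL/kg and 33-58% at 219 mL/kg.
- Clearance de-indexed for an assumed body surface area of about 1.97 m² at 80 kg: 23-48% (GFR 30 to 15).
- Adding 11 mL/min non-renal clearance at 80 kg: 18-33% (GFR 29 to 15).
- Contrast with healthy function at 80 kg: 8% at GFR 60 and 2% at GFR 90.

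**Step 2: precision of the clearance.** Take a log-linear fit to the samples from 120 min on, with CL = dose × slope / exp(intercept) and assay error s on the log scale. The delta method gives

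CV ≈ s × √[1/n + (t̄ − 1/k)² / Sxx], with k = CL/V.

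- Samples to 560 min: n = 6, t̄ = 256.7, Sxx = 134,133.
- With 1280 min added: n = 7, t̄ = 402.9, Sxx = 1,031,743.

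At 80 kg and GFR 15, 1/k = 880 min. With s = 5% the CV is 5 × √(0.167 + 2.897) = 8.8%; with the 24 h sample it is 5 × √(0.143 + 0.221) = 3.0%. The other cases follow in the same way:

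| Case (80 kg) | Assay error | To 560 min | With 24 h |
|---|---|---|---|
| GFR 15 | 2% / 5% | 3.5% / 8.8% | 1.2% / 3.0% |
| GFR 22.5 | 5% | 5.0% | 2.1% |
| GFR 29 | 2% / 5% | 1.4% / 3.4% | 0.8% / 1.9% |
| GFR 15 + 11 non-renal | 5% | 4.0% | 2.0% |
| GFR 29 + 11 non-renal | 5% | 2.3% | 1.9% |

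**Step 3: effect on the limits of agreement.** Suppose FAST itself had 5% error (an assumption). The 95% limits are 1.96 × √(CV² + 5²). With 5% assay error and no non-renal clearance they go from about ±20% to ±11% at GFR 15, and from ±11.9% to ±10.5% at GFR 29.

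**Step 4: would iohexol be measurable at 24 h?** The dose is 5 × 647 = 3235 mg (Table 7.2), or about 245 µg/mL in 13.2 L at time zero. At 1280 min the model leaves about 57 µg/mL at GFR 15 and 15 µg/mL at GFR 29. The existing schedule already asks the assay to read about 5 µg/mL at 560 min in a healthy subject with GFR 90.

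**The case against.** Much of the size rests on choices the documents do not make. A reader might settle on the 80 kg row and report 29-53% as the extrapolated share. That needs an undocumented weight, indexed eGFR used as absolute clearance, and no non-renal clearance, although Section 3.5 shows total clearance above renal clearance and says gallbladder excretion may rise in severe impairment. The 11 mL/min comes from the 16-adult data and is an assumption in these patients, but so is zero. This objection stands: the share has to be given as a range.

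A reader might also say that only about one half-life is observed. At 80 kg, 560 minutes is 0.9 half-lives at GFR 15 but 1.8 at GFR 29; only the 120-560 minute fitting window, at 0.7 to 1.4, fits that description.

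A third tempting reading is that reference noise matches the protocol's own agreement target. Section 3.4.3 does say "It was expected that the FAST mGFR measurements would be within 10% in the lower GFR groups", but as a Phase 2a expectation. Nothing in this study is judged against it, and the noise approaches that size only near GFR 15 with 5% assay error. If FAST had 10% error, the limits at GFR 15 would move only from ±26% to ±20%. With 8 patients, each estimated limit carries a 95% interval of about ±1.5 SD in any case.

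Finally, the schedule already runs longer than the 6-hour Phase 2a test, and the comparison is secondary, descriptive and without hypotheses. These points lower the priority. None removes the gain in Cohort 4, which appeared in every variant tried.

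**Conclusion.** The concern holds as a cheap design improvement for Cohort 4. Depending on weight and GFR, roughly 20-60% of the reference AUC lies beyond the last iohexol sample at 165 mL/kg, or 18-33% at 80 kg with non-renal clearance added. Using the 24 h draw gives about 2-31% without non-renal clearance. The precision gain is material near GFR 15 and modest near GFR 29; with non-renal clearance and 5% assay error it is a fall from about 2-4% to 2%.

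All of this rests on a one-compartment model, assumed weights and assay error, and an estimator that the documents leave undefined. It does not support a claim that the Cohort 4 comparison is invalid.

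Nor does it support the same request for Cohort 3. At GFR 45 and 80 kg with 3% assay error, the CV moves only from 1.3% to 1.2%; only patients close to 30 mL/min would gain as much as those at the top of Cohort 4.

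**What to change.** In Protocol Table 2.6 and SAP Table 1.6, mark the 24 h draw, and optionally the 32 h draw, as an iohexol PD sample for Cohort 4. State in the SAP how iohexol clearance is calculated and that the added sample enters the terminal-phase fit.

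The cost is about 8 extra assays per time point, a few mL more blood at a draw already scheduled, and a small edit to each table. No visit or venipuncture is added, and the rule in the note to Table 2.6 on the order of VFI and iohexol samples can apply unchanged.
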